### **Secondary outcomes analysis**

All secondary binary outcomes will be estimated as with the primary outcome and summarized with risk differences, risk ratios and 95% confidence intervals.

The secondary outcome of HIV viral suppression at different thresholds will be analyzed similar to the primary outcome - as a non-inferiority comparison followed by superiority if non-inferiority is established but no sensitivity analyses or effect modification will be done.

The secondary endpoints of retention in care, engagement in care, disengagement from care, lost to follow-up, and ART initiation within 7 or 28 days after enrollment will be assessed for superiority in the ITT population.

Non-traumatic mortality, hospitalizations, SAEs, AESIs and incidence of TB will be summarized descriptively as events are expected to be rare.

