### 2.2 Objectives

To compare two approaches for the timing of ART initiation in PLHIV with presumptive TB but no signs of CNS disease (“ART first” versus “TB results first”) with regard to HIV viral suppression, engagement in care, serious adverse events (SAEs) and adverse events (AEs) consistent with TB-IRIS (AEs of special interest, AESIs) in a randomized trial reflecting routine primary and secondary care setting in Lesotho and Malawi .

**Primary objective:** To assess if same-day ART initiation (“ART first”) is non-inferior to rapid ART initiation (“TB results first”) with regard to HIV viral suppression (VL <400 copies/mL) 26 weeks after enrolment among PLHIV with presumptive TB

**Secondary objectives:** To compare in PLHIV with presumptive TB same-day ART initiation (“ART first”) versus rapid ART initiation (“TB results first”) with regard to:

- retention in care
- disengagement from care
- unsuppressed VL
- safety outcomes (SAEs, and AESIs)
- TB incidence
- proportion of PLHIV with rapid ART initiation (within 7 and within 28 days)

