## Endpoints

As per the protocol, the primary endpoint of the trial is:

- HIV viral suppression <400 copies/mL 26 (22 – 40) weeks after enrolment (obtained from routine laboratory reports at study facility, from laboratory reports of referral facility in case of transfer out, or from dried blood spot (DBS) sample for participants without documented clinic visit but found during home visit tracing)

As per the protocol, the secondary endpoints of the trial are:

- Retention in care 26 (22 – 30) weeks after enrolment, defined as a documented ART clinic visit between 22 and 30 weeks after enrolment
- Engagement in care 26 (22 – 30) weeks after enrolment, defined as reporting regular ART intake, irrespective if a documented visit took place between 22 and 30 weeks after enrolment
- Disengagement from care 26 (22 – 30) weeks after enrolment, defined as non-engaged in care but reached through patient tracing
- Lost to follow-up 26 (22 – 30) weeks after enrolment, defined as non-retained in care and not reached through tracing
- Non-traumatic mortality, SAEs, and AESIs (see section 7.1.3 for definition) during the first 30 weeks after enrolment
- Incidence of TB disease (microbiologically confirmed and/or clinical diagnosis) during the first 30 weeks after enrolment, defined as any TB diagnosis after enrolment not classified as prevalent TB at enrolment (see definition below under exploratory endpoints)
- HIV viral suppression at 26 (22 – 40) weeks using different thresholds (<20 copies/mL; <100 copies/mL; <1000 copies/mL)
- ART initiation within 7 and within 28 days after enrolment

As per the protocol, the exploratory endpoints of the trial are:

- Clinical characteristics of participants with non-traumatic hospitalizations and deaths in PLHIV with presumptive TB
- Prevalence of active TB diagnosed at enrolment, defined as TB diagnosed clinically or microbiologically through the TB investigations initiated at enrolment and completed up to a maximum of 28 days after enrolment.

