## 4. Statistical principles

### 4.1 Confidence intervals and p-values

Statistical tests and confidence intervals will be two-sided. Estimates will be presented with 95% confidence intervals. P-values will be presented where appropriate. No adjustments will be made for multiple testing nor interim analyses. Interpretations will be based on the strength of evidence of effect size and consistency of results for related outcomes.

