## 4.3 Analysis populations

As per the protocol (2), all analyses will be done by the trial statistician using R (the R Foundation for Statistical Computing) or Stata (version 18, Stata Corporation, Austin/Texas, USA). Analysis will follow CONSORT guidelines. Primary analyses for the non-inferiority comparison will be performed on both the ITT and per protocol (PP) sets (3).

Our approaches for the primary outcome are further detailed in the context of the estimands framework in Tables 2a and 2b (4).

For secondary outcomes related to VL (achieving viral suppression defined by other thresholds), we will employ similar methods as for the primary outcome (both superiority and non-inferiority comparisons).

For the remaining secondary outcomes, we will employ similar methods as for the primary outcome but under the superiority comparison only.

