**Table 2a. Estimand framework: primary outcome for superiority comparisons, resembling intention to treat approach [1].**

Estimand attribute	Definition	Comments
Population	Individuals aged 12 years or older, testing HIV-positive or known to be HIV-positive and not taking ART, with one or more TB symptoms according to WHO four-symptom screening (4WSS), who would not die from a trauma-related cause before having the endpoint measured.	Exclusion of individuals considered too ill to follow standard care (needing admission or referral, CNS symptoms, or a positive CrAg test), pregnant women, or those taking TB treatment were excluded as written in the protocol. Exclusion of individuals who die from trauma-related causes before having the endpoint measured.
Treatment conditions	Same day ART start (“ART first”) vs. ART start once TB confirmed or refuted (“TB results first”)	
Endpoint	HIV viral load measured and suppression <400 copies/mL 26 (22 – 40) weeks after enrolment and did not die from a non-trauma-related cause prior to 40 weeks.	Endpoint clarified to include those who die from a non-trauma-related cause or were LTFU without a VL measurement as “failures”, i.e. did not achieve viral suppression.
Summary measure	Risk differences. We will also report odds ratios and risk ratios.	
Handling of intercurrent events (IE) [2]		
Ineligible	“Principal stratum” approach	Individuals found to be ineligible after randomization are excluded from the analysis under the assumption that their eligibility would be independent of the randomization allocation
Failure to initiate assigned treatment according to protocol	“Treatment policy” approach	The IE are defined as 1)not offering same-day ART in the “ART first” arm and 2) offering ART start prior to completing TB investigation in the “TB results first” arm. This IE is ignored and considered part of the intention to treat strategy
Failure to initiate ART	“Treatment policy” approach	This IE applies only to the “TB results first” arm and is ignored and considered part of the intention to treat strategy.
Discontinuation of ART	“Treatment policy” approach	This IE is ignored and considered part of the intention to treat strategy.
Transfer to another facility	“Treatment policy” approach	This IE is ignored and considered part of the intention to treat strategy.

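### SAP 6.2 appears to leave deaths, SAEs, AESIs and incident TB without a between-arm estimate and interval, although comparing the arms on safety and TB incidence is a secondary objective

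*SAP*

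**What the plan says.** SAP 2.2 words the secondary objectives as comparisons: "To compare in PLHIV with presumptive TB same-day ART initiation (“ART first”) versus rapid ART initiation (“TB results first”) with regard to". The list that follows includes safety outcomes (SAEs and AESIs) and TB incidence; protocol 3.1.2 has the same list. The SAP's Endpoints section names as secondary endpoints "Non-traumatic mortality, SAEs, and AESIs (see section 7.1.3 for definition) during the first 30 weeks after enrolment", and lists incident TB beside them. Hospitalization is not listed separately there, but it is one of the SAE criteria.

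Three statements then bear on how these outcomes are analysed:

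- SAP 6.2, Secondary outcomes analysis, first sentence: "All secondary binary outcomes will be estimated as with the primary outcome and summarized with risk differences, risk ratios and 95% confidence intervals".
- SAP 4.3: "For the remaining secondary outcomes, we will employ similar methods as for the primary outcome but under the superiority comparison only". The primary method's summary measure in Table 2a is "Risk differences. We will also report odds ratios and risk ratios", and SAP 4.1 adds "Estimates will be presented with 95% confidence intervals".
- SAP 6.2, Secondary outcomes analysis, last sentence: "Non-traumatic mortality, hospitalizations, SAEs, AESIs and incidence of TB will be summarized descriptively as events are expected to be rare".

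The outcomes that SAP 6.2 names for superiority assessment in the ITT population are the care-engagement and ART-initiation endpoints; no safety or TB outcome is among them. SAP 6.5 (Harms) refers back to 6.2 and adds only that safety outcomes are reported by randomized arm. The opening of SAP 6.2 requires numbers and percentages by arm for categorical outcomes.

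**The concern.** An analyst who follows the first sentence of the secondary-outcomes section produces a risk difference and interval for SAEs, AESIs, non-traumatic death and incident TB. One who follows the last sentence may produce a table of counts and percentages only. The second reading leaves a stated comparative objective without an estimate of the difference or of its uncertainty.

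This matters more here than in most strategy trials. Protocol 11.2 describes the trade-off as more IRIS risk under ART first against more pre-ART attrition under TB results first, and says the balance is unknown. The attrition side gets a margin, a confidence interval and a figure. If the harm side gets only counts, a reader of a non-inferior primary result is not told how large a safety excess the data still allow, and sparse counts are easily read as showing no difference.

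**Working it through.** **1. Fix the sample size.** Inputs from SAP 3.3: 75% suppression assumed (taken as equal in both arms, as in the protocol synopsis), margin 10 points, one-sided alpha 0.025, power 80%.

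n per arm = (1.960 + 0.842)² × 2 × 0.75 × 0.25 / 0.10² = 294.3, rounded up to 295, or 590 in total. This reproduces the plan's figure. SAP 3.3 says secondary endpoints played no part in it.

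**2. Compare the rules.**

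| Place | Rule for safety and TB outcomes | Exception stated? |
|---|---|---|
| SAP 6.2, secondary outcomes, first sentence | RD, RR and 95% CI | No |
| SAP 4.3 | Methods similar to the primary outcome, superiority only; RD and CI follow by way of Table 2a and SAP 4.1 | No |
| SAP 6.2, secondary outcomes, last sentence | Descriptive summary, because rare | This sentence would be the exception |
| SAP 6.5 | By arm; refers to 6.2 | No contrast mentioned |
| Protocol 9.2.2 | RD and 95% CI for secondary endpoints, then the same descriptive sentence | Same structure |

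**3. Does rarity rule out an interval?** The documents give no expected event rates, so the counts below are assumptions chosen to cover a range. All 295 participants per arm are taken as having known status.

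Wilson limits for x events of n, with p = x/n and z = 1.960:

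[p + z²/2n ± z√(p(1−p)/n + z²/4n²)] / (1 + z²/n)

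Newcombe interval for d = p₁ − p₂, where (l, u) are the Wilson limits in each arm:

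- lower = d − √[(p₁ − l₁)² + (u₂ − p₂)²]
- upper = d + √[(u₁ − p₁)² + (p₂ − l₂)²]

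Example, 15 v 9 events: p₁ = 5.08% (Wilson 3.11 to 8.22), p₂ = 3.05% (Wilson 1.61 to 5.70), d = 2.03.

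- Lower = 2.03 − √(1.97² + 2.65²) = −1.3
- Upper = 2.03 + √(3.14² + 1.44²) = +5.5

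| Assumed events (of 295 v 295) | Risk difference, points | Newcombe 95% CI |
|---|---|---|
| 0 v 0 | 0.0 | −1.3 to +1.3 |
| 3 v 3 | 0.0 | −2.0 to +2.0 |
| 9 v 9 | 0.0 | −3.0 to +3.0 |
| 15 v 9 | +2.0 | −1.3 to +5.5 |
| 15 v 15 | 0.0 | −3.7 to +3.7 |
| 30 v 30 | 0.0 | −5.0 to +5.0 |
| 30 v 15 | +5.1 | +0.8 to +9.5 |

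An interval exists at every count, including no events in either arm. The log-link model of SAP 6.2 can fail when an arm has no events, which is a reason to name another method.

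**4. Does rarity rule out a test?** Largely, yes. Power to detect a doubling of risk at 295 per arm (two-sided 5%, normal approximation) is 17%, 30%, 42%, 64% and 93% for assumed control-arm risks of 1%, 2%, 3%, 5% and 10%. The SAP's reason therefore supports leaving out the hypothesis test. It does not support leaving out the estimate and its interval.

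**The case against.** The strongest reply is that there is no real contradiction. The secondary-outcomes section gives a general rule and then specific instructions by outcome group; a specific sentence with its own reason reads naturally as an exception. Protocol 9.2.2 has the same sequence and the same descriptive sentence, so the choice was made before the SAP. This stands as the likely intention. It does not reach SAP 4.3, which has no carve-out, and it does not supply the missing contrast for the objective.

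Second, the SAP does not use the word for descriptive summary to exclude effect estimates: in SAP 6.2 the primary outcome's effect estimates by country are themselves to be presented descriptively. On that reading the first sentence still applies, and the last means only that these outcomes are not tested. This also stands as a possible reading. A reader might infer that the SAP definitely withholds any between-arm estimate for safety; the text does not establish that.

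Third, a reader might infer that two separate SAP sections expressly promise risk differences with intervals for these outcomes. They do not. One statement opens the same section that later makes the exception; the other, in 4.3, reaches risk differences and intervals only by reference to the primary method.

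Fourth, counts by arm will be published, so anyone can compute an unadjusted interval. True, but that leaves the trial's own objective to its readers.

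Fifth, an interval can reassure too much. SAP 6.1 and protocol 7.1.4 say AESIs are not asked about at the week-26 visit or during tracing, and events in people lost to follow-up may be unknown. Treating all 295 as observed counts unknowns as event-free. This objection stands and shapes the fix.

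**Conclusion.** The point holds as a mismatch between a comparative objective and an analysis rule that, on its likely reading, gives no comparison. What is missing is the between-arm difference and its uncertainty, not the data by arm. The descriptive sentence is probably deliberate, and the SAP leaves open whether it excludes an estimate or only a test; the wording should settle this.

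The size of the issue is the information forgone. Under the assumed counts, intervals run from about ±1 to ±5 points where the arms are equal, and an excess of 30 v 15 would have an interval above zero. These figures rest on 295 per arm, complete 30-week status and invented event counts; they show what can be computed, not what the trial will find. Some intervals will be wide: 15 v 9 is compatible with a slight benefit or a sizeable harm. No primary result, error rate or decision rule changes. The change should be made because it is cheap and answers a stated objective.

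**What to change.** In the last sentence of SAP 6.2, Secondary outcomes analysis, state that non-traumatic mortality, hospitalization, any SAE, adjudicated AESI and incident TB will be reported as n (%) by arm plus the risk difference with a 95% interval by a small-count method (Newcombe or Miettinen-Nurminen), with no p-value and no superiority test. These intervals would be unadjusted unless a country-stratified version is chosen; say which.

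Also:

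- State the denominator for each outcome, and report by arm the number of participants whose 30-week status is unknown.
- Note beside the AESI interval that it reflects sampling error only, because AESIs are not solicited at the week-26 visit or in tracing.
- Bring SAP 4.3, the first sentence of the secondary-outcomes section and SAP 6.5 into line, and record that this clarifies protocol 9.2.2.

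The cost is SAP wording and a few lines of code, with wide intervals for some outcomes. It needs no new data and no change to the primary analysis.

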### **6.3 Missing data**

Missing baseline and outcome data will be summarized by study arm. Where applicable, percentages will be of non-missing values.

In the case of missing VL for the primary endpoint, when no information is available, the participant is considered to have failed (see Table 2a and 2b). However, in the case where a VL result was not available, but information about ART refills is available, we will consider using multiple imputation in a sensitivity analysis if the numbers of these cases is sufficient to warrant the additional complexity.

### **6.4 Additional analyses**

Analyses for sub-studies will be described elsewhere.

### **6.5 Harms**

Safety data are included as secondary endpoints (see section 6.2).

We will report by randomized arm on the number of pregnancies and safety outcomes.

## 6.6 Statistical software

Analyses will be conducted in Stata version 18 (15).

## 8. Shell tables and figures

Presented below are the shell tables and figures for the participant flow and baseline characteristics, to illustrate the variables included. Further tables will be included in the report to present the analyses described above, including outcomes and safety data.

## 8.1 Flowchart.

## 8.2 Baseline characteristics by randomized arm.

	TB first	ART first	Total
Number randomized			
Country			
Malawi			
Lesotho			
ART status			
Naïve			
Previously treated			
Demographics and socio-economics			
Sex, female			
Age, years			
Marital status			
Occupation			
Highest level of education completed			
Literate			
Mode of travel to the clinic			
Time to reach clinic (min)			
Cost to reach clinic			
Malawi (Malawi Kwacha)			
Lesotho (Loti/Rand)			
Wealth steps			
TB symptoms			
Cough			
Night sweats			
Losing weight			
Fever			
Health status			
Self-rated health status			
Karnofsky score			
Time since HIV diagnosis			
WHO stage			
CD4 cell count			
Vitals			
Weight, kg			
BMI			
Respiratory rate			
Heart rate			
Temperature			
Oxygen saturation			

Results are number (column % of those with non-missing data) for categorical variables and median (IQR) [range] for continuous variables.
